7.3 STUDY MEDICATION ACCOUNTABILITY

The PI, as study sponsor, will ensure maintenance of complete and accurate records of the receipt, dispensation, and disposal or return of all study drug in accordance with 21 CFR, Part 312.57 and 312.62 and MacroGenics requirements.

All unused remaining product at the end of the study should be disposed of at the study site according to institutional standard operating procedure. If there is no standard operating procedure at the site for drug destruction, study drug will be returned to MacroGenics as directed.

7.4 DATA COLLECTION

The study coordinator and investigators are responsible for ensuring that the eligibility checklist is completed in a legible and timely manner for every patient enrolled in the study, and that data are recorded on the appropriate forms and in a timely manner. Any errors on source data should be lined through, but not obliterated, with the correction inserted, initialed, and dated by the study coordinator or PI. All source documents will be available for inspection by the FDA and the Georgetown University IRB.

8. ETHICAL CONSIDERATIONS

8.1 COMPLIANCE WITH LAWS AND REGULATIONS

Patients who comply with the requirements of the protocol, are tolerating study treatment, and may be receiving benefit will be offered dosing beyond Cycle 1 at the investigator's discretion after a careful assessment and thorough discussion of the potential risks and benefits of continued treatment with the patient. Such patients may have the option to receive treatment as long as they continue to experience clinical benefit in the opinion of the investigator until the occurrence of unacceptable toxicity,

symptomatic deterioration attributed to disease progression, or any of the other reasons for treatment discontinuation.

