3.1.1 Study schema & overview of study design

This is an open label phase 2, multi-center, single arm study evaluating the efficacy of MGC018 in patients with relapsed or refractory ES-SCLC. Our cohort will enroll patients with ES-SCLC who experience progression during or following treatment with platinum-based chemotherapy. For full detailed inclusion/exclusion criteria, see section 4.1.

Patients enrolled will receive MGC018 at 2.0 mg/kg every 28 days continuously until completion of 8 cycles, disease progression, or unacceptable toxicity. Tumor assessment will be done every 2 cycles. The primary endpoint of the study will be assessed by ORR utilizing RECIST v1.1.

Key secondary endpoints will include incidence of adverse events per CTCAE v5.0, DOR, PFS, and OS. In an exploratory fashion, we plan to evaluate efficacy according to expression of B7-H3 on tumor tissue and blood-based biomarkers. Pre-treatment biopsy will be obtained to assess expression of B7-H3 on tumor tissue. If biopsy is not considered safe and medically feasible by the investigator, the patient may be approved for enrollment after consultation the principal investigator. In this case, we will obtain archival tissue if available. Expression of B7-H3 and other immune markers on tumor tissue will be assess using Imaging Mass Cytometry (Fluidigm platform) and correlated with treatment outcomes such as ORR, PFS, and OS. Blood samples will be obtained for biomarker analysis at day 1 of cycle 1, on day 1 of cycle 3, and at time of progression.

Figure 3 – Study Schema (N=17)

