3.1.4 PK and ADA data

Blood samples will be regularly collected and submitted for PK and anti-drug antibody (ADA) assays. Support for these assays will be provided by MacroGenics. Total and ADC PK assays as well as ADA assays will be performed on the serum. Samples for PK data will be collected pre- and post-infusion as

well as on day 15 of cycles 1 and 2 then pre- and post-infusion for cycles 3 through 5 as well as every 3 cycles for cycles 6 through 12. ADA assays will be performed on samples collected pre-infusion as well as on day 15 of cycle 1 then pre-infusion for cycles 2 through 5 and every 3 cycles for cycles 6 through 12. PK and ADA testing will be obtained at the EOTV. PK and ADA testing may be performed at the time of any IRR.

Table 2. PK and ADA collection schedule

| Cycle | Day | Timepoint | Window | PK: Total and ADC (serum) | ADA: (serum) |
|------------------|-----|-----------------|---------|------------------------------------|-----------------|
| 1 | 1 | Pre-infusion | N/A | X | X |
| 1 | 1 | End of infusion | +10 min | X | |
| 1 | 15 | Day 15 | N/A | X | X |
| 2 | 1 | Pre-infusion | N/A | X | X |
| 2 | 1 | End of infusion | +10 min | X | |
| 2 | 15 | Day 15 | N/A | X | |
| 3, 4, and 5 | 1 | Pre-infusion | N/A | X | X |
| 3, 4, and 5 | 1 | End of infusion | +10 min | X | |
| 6, 9, and 12 | 1 | Pre-infusion | N/A | X | X |
| 6, 9, and 12 | 1 | End of infusion | +10 min | X | |
| IRR ^a | N/A | N/A | N/A | X | X |
| EOTV | N/A | EOTV | N/A | X | X |

Note: Actual start of infusion times, EOI times, and PK/ADA sample collection times will be recorded on the eCRFs. Do not collect PK samples from infusion port. Pre-infusion PK samples may be collected before start of infusion on visit day (dosing day) or day before infusion. When collecting multiple samples, collect the PK sample first.

^aPK and ADA samples may be obtained at additional time points in participants who experience signs and symptoms of IRR. Samples should be obtained as soon as possible after onset of IRR, if feasible.

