4.2.2.1 MGC018

MGC018 will be administered by IV infusion at a dose of 2.0 mg/kg on Day 1 of each 28-day cycle until completion of cycle 8, unacceptable toxicity, or loss of clinical benefit as determined by the investigator after an integrated assessment of radiographic and biochemical data, local biopsy results (if available), and clinical status (see Section 3.1.1 for details). For subjects weighing ≥ 100 kg the doses will be based on 100 kg for these subjects. To decrease the frequency and severity of palmar-plantar erythrodysesthesia (PPE) and effusions, prednisone 40 mg will be given twice daily for three days of each cycle starting the evening after each infusion for a total of 6 doses. In addition, patients will be provided with a strong or moderate-strength topical steroid cream to be applied as prescribed to the hands and soles prophylactically for the first 12 weeks of therapy.

Administration of MGC018 will be performed in a monitored setting where there is immediate access to trained personnel and adequate equipment and medicine to manage potentially serious reactions. For anaphylaxis precautions, see Appendix 3. MGC018 infusions will be administered per the instructions outlined in Table 3.

Table 3. Administration of first and subsequent MGC018 infusions

| Study Drug | First Infusion | Subsequent Infusions |
|-----------------|---|--|
| MGC018 infusion | 
Premedication with acetaminophen (650mg to 1000 mg), diphenhydramine 50 mg PO or IV, famotidine 40 mg PO or 20 mg IV, and corticosteroid (e.g | 
If the patient experienced an infusion-related reaction (IRR) with any previous infusion, additional premedication may also be considered. |

| | | |
|---|---|---|

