4.4.6 Laboratory, biomarker, and other biological samples

Samples for the following laboratory tests must be reviewed prior to dosing. See Appendix 1 for specifics related to which lab tests are required at specific time points during study ("screening" vs "on treatment", etc.):

- Hematology: WBC count, RBC count, hemoglobin, hematocrit, platelet count, and differential count (neutrophils, eosinophils, basophils, monocytes, lymphocytes, other cells).
- Chemistry panel (serum or plasma): bicarbonate or total carbon dioxide (if considered standard of care for the region), sodium, potassium, chloride, glucose, BUN or urea, creatinine, total protein, albumin, phosphorus, calcium, total bilirubin, alkaline phosphatase, ALT, and AST.
- Coagulation: INR, and aPTT (screening only).
- Thyroid function testing: thyroid-stimulating hormone (TSH), free triiodothyronine (T3) (or total T3 for sites where free T3 is not performed), and free thyroxine (also known as T4) at screening only. Repeat thyroid function testing as clinically indicated.

- Pregnancy test

All women of childbearing potential will have a serum pregnancy test at screening, and during the study, urine pregnancy tests will be performed at every cycle and after study treatment is discontinued. If a urine pregnancy test is positive, it must be confirmed by a serum pregnancy test.

A woman is considered to be of childbearing potential if she is postmenarchal, has not reached a postmenopausal state (≥ 12 continuous months of amenorrhea with no identified cause other than menopause), and has not undergone surgical sterilization (removal of ovaries and/or uterus).

The following samples will be sent to the PI or a designee for analysis or banked for subsequent analysis:

- Peripheral blood to be obtained on day 1 of cycle 1, day 1 of cycle 3, and at progression
- Prior to treatment initiation, tumor tissue will be obtained following progression on most-recent therapy for determination of biomarker status including exploratory correlative analyses. Please refer to the lab manual for details. **If a biopsy is not feasible and/or safe, it may be waived after discussion with the principal investigator.** In this case, we will obtain archival tissue if available.

For sampling procedures, storage conditions, and shipment instructions, see the laboratory manual.

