^ba woman is defined as “of childbearing potential” if she is postmenarchal and has not reached post-menopausal state (≥12 continuous months of amenorrhea without identified cause other than menarche), and has not undergone surgical sterilization (removal of ovaries and/or uterus).

^cMust be performed ≥5 days prior to study treatment administration. If a biopsy is not feasible and/or safe, it may be waived after discussion with the principal investigator. In this case, we will obtain archival tissue if available.

^dimaging assessments performed as standard-of-care prior to obtaining study informed consent and within 28 days of study treatment initiation do not have to be repeated at screening.

^eMRI brain is required to confirm or refute diagnosis of CNS metastases in the event of equivocal CT scan.

Table 2 – Study Calendar

| Procedure | Treatment Cycles (28-day cycle) | | | Treatment Discontinuation | Follow-up |
|----------------------------|------------------------------------|---------------------------------|-----------------------------------|-------------------------------|-----------|
| | Cycle 1 D1 and D15 (±3 days) | Cycle 2 D1 and D15 (±3 days) | Subsequent Cycles D1 (±3 days) | ≤30 days after last treatment | |
| Clinical Assessment | | | | | |
| ECOG PS | X | X | X | X | |
| Vital Signs ^a | X | X | X | X | |

| | | | | | |
|---|------------------|---|------------------|---|---|
| Weight | X | X | X | X | |
| Laboratory Tests^b | | | | | |
| CBC w/ diff | X | X | X | X | |
| Chemistries ^c | X | X | X | X | |
| Imaging Response Assessments^d | | | X | | |
| Correlative Studies | | | | | |
| Peripheral blood ^e | X (only on C1D1) | | X (only on C3D1) | X | |
| Tumor biopsy ^f | | | | X | |
| Other Assessments | | | | | |
| Con Meds ^h | X | X | X | X | |
| Adverse Events ⁱ | X | X | X | X | X |
| Study Treatment administration | X | X | X | | |
| Survival follow-up and anti-cancer treatment ^j | | | | | X |

^aincludes temperature, respiratory rate, heart rate, and blood pressure. For the first infusion, vital signs should be measured within 60 minutes prior to the infusion of MGC018, every 15 (\pm 5) minutes during MGC018 infusion if clinically indicated, and 30 (\pm 10) minutes after the infusion. For subsequent infusions, vital signs should be measured within 60 minutes prior to the infusion and, if clinically indicated or if symptoms occurred during the previous infusion, during and 30 (\pm 10) minutes after the infusion.

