Table 4 – Calendar of Peripheral Blood draws for PK and ADA testing

| Cycle | Day | Timepoint | Window | PK: Total and ADC (serum) | ADA: (serum) |
|------------------|-----|-----------------|---------|------------------------------------|-----------------|
| 1 | 1 | Pre-infusion | N/A | X | X |
| 1 | 1 | End of infusion | +10 min | X | |
| 1 | 15 | Day 15 | N/A | X | X |
| 2 | 1 | Pre-infusion | N/A | X | X |
| 2 | 1 | End of infusion | +10 min | X | |
| 2 | 15 | Day 15 | N/A | X | |
| 3, 4, and 5 | 1 | Pre-infusion | N/A | X | X |
| 3, 4, and 5 | 1 | End of infusion | +10 min | X | |
| 6, 9, and 12 | 1 | Pre-infusion | N/A | X | X |
| 6, 9, and 12 | 1 | End of infusion | +10 min | X | |
| IRR ^a | N/A | N/A | N/A | X | X |
| EOTV | N/A | EOTV | N/A | X | X |

Note: Actual start of infusion times, EOI times, and PK/ADA sample collection times will be recorded on the eCRFs. Do not collect PK samples from infusion port. Pre-infusion PK samples may be collected before start of infusion on visit day (dosing day) or day before infusion. When collecting multiple samples, collect the PK sample first.

^aPK and ADA samples may be obtained at additional time points in participants who experience signs and symptoms of IRR. Samples should be obtained as soon as possible after onset of IRR, if feasible.

Appendix 1

Calculation of Creatinine Clearance Using the Cockcroft-Gault Formula

Creatinine Clearance (men) = $(140 - \text{Age}) \times \text{Lean Body Weight [kilograms]}$

Serum Creatinine (mg/dL) $\times 72$

Creatinine Clearance (women) = $0.85 \times (140 - \text{Age}) \times \text{Lean Body Weight [kilograms]}$

Serum Creatinine (mg/dL) $\times 72$

Source: Gault MH, Longerich LL, Harnett JD, et al. Predicting glomerular function from adjusted serum creatinine (editorial). Nephron 1992;62:249.

Appendix 3

Anaphylaxis Precautions

EQUIPMENT NEEDED

- Monitoring devices: ECG monitor, blood pressure monitor, oxygen saturation monitor, and thermometer
- Oxygen
- Epinephrine for intravenous, intramuscular, and endotracheal administration in accordance with institutional guidelines
- Antihistamines
- Corticosteroids
- Intravenous infusion solutions, tubing, catheters, and tape

PROCEDURES

In the event of a suspected anaphylactic reaction during study treatment infusion, the following procedures should be performed:

1. Stop the study treatment infusion.
2. Call for additional medical assistance.

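### The protocol stops treatment at 8 cycles, but the PK/ADA schedule runs to cycle 12 and Section 8.1 sets no limit; the passages need reconciling

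*Combined protocol and SAP*

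**What the plan says.** **Duration, treatment sections.** Section 3.1.1 gives dosing "every 28 days continuously until completion of 8 cycles, disease progression, or unacceptable toxicity". Section 3.3.1 repeats the 8-cycle end point. Section 4.2.2.1 says "MGC018 will be administered by IV infusion at a dose of 2.0 mg/kg on Day 1 of each 28-day cycle until completion of cycle 8", or earlier for toxicity or loss of benefit.

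**Duration, elsewhere.** Section 8.1 concerns patients who are tolerating treatment and may be benefiting: "Such patients may have the option to receive treatment as long as they continue to experience clinical benefit in the opinion of the investigator". It ends treatment for toxicity, symptomatic deterioration or another discontinuation reason. Section 4.5.1 lists seven such reasons, and completing 8 cycles is not one of them.

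**PK/ADA sampling.** Section 3.1.4 plans samples "every 3 cycles for cycles 6 through 12". Appendix 1 Table 4, like Table 2 in Section 3.1.4, carries the row "6, 9, and 12 | 1 | Pre-infusion | N/A | X | X" and a matching end-of-infusion row for the same cycles.

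**Study calendar (Appendix 1 Table 2).** The first treatment column is headed "Cycle 1 D1 and D15 (±3 days"), and the second is headed the same way for cycle 2. The treatment row reads "Study Treatment administration | X | X | X", with no day given. The correlative blood row of the same table does limit its ticks to a named day.

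**Pregnancy testing.** Section 4.4.6 states that "urine pregnancy tests will be performed at every cycle and after study treatment is discontinued", and refers to Appendix 1 for the timing of laboratory tests. Appendix 1 Table 1 lists the screening test. The study calendar has no pregnancy-test row.

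**The concern.** Treatment duration is a core instruction, and here it can be read in two ways. An end-of-infusion sample at cycle 12 presupposes an infusion at cycle 12, which the treatment sections rule out. A site with a patient still benefiting at the end of cycle 8 can cite Sections 3.1.1, 3.3.1 and 4.2.2.1 for stopping, or Section 8.1 and the PK/ADA tables for continuing. No passage says which prevails.

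The trial is small (up to 17 patients) and has at least four named sites. If sites resolve the point differently, exposure and cumulative toxicity will differ between the longest-treated patients for reasons unrelated to their disease. Part of the tabulated PK/ADA collection would also be missing by construction, and would need explaining at analysis as something other than missed samples.

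The two calendar gaps matter because Section 4.4 makes Appendix 1 the schedule of activities and requires every activity in it to be performed and documented.

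**Working it through.** **1. Figures the plan states.** The plan gives no figure for this point. The only stated figures it might touch are the Simon error rates. With 9 patients in stage 1, a stop at 0 responses, 17 in total and rejection at 3 or more:

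P(reject | p) = Σ over x = 1 to 9 of C(9,x) p^x (1−p)^(9−x) × P[Bin(8,p) ≥ 3−x]

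This gives 0.0466 at p = 0.05 and 0.8122 at p = 0.25, matching the stated 4.7% and 81.2%. Treatment duration does not enter the calculation.

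**2. When the cycles fall.** With 28-day cycles and no delays, Day 1 of cycle c is study day 28(c−1)+1.
- Cycle 8: 28×7+1 = day 197, the last dose under the limit. Cycle 8 ends on day 8×28 = 224, about 7.4 months.
- Cycle 9: 28×8+1 = day 225.
- Cycle 12: 28×11+1 = day 309.

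Both of the last two fall after the limit.

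**3. Scheduled PK/ADA per patient who stays on treatment**, leaving out reaction-triggered and end-of-treatment samples:

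| Visits | PK | ADA |
|---|---|---|
| C1D1, C1D15 | 2+1 = 3 | 1+1 = 2 |
| C2D1, C2D15 | 2+1 = 3 | 1+0 = 1 |
| C3, C4, C5, C6 (Day 1) | 4×2 = 8 | 4×1 = 4 |
| **To cycle 8: 8 visits** | **14** | **7** |
| C9, C12 (Day 1) | 2×2 = 4 | 2×1 = 2 |
| **As tabulated: 10 visits** | **18** | **9** |

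So 2 of 10 visits, 4 of 18 PK samples and 2 of 9 ADA samples cannot be obtained under the limit. After cycle 6 the only routine sample left is the one at the end-of-treatment visit.

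**4. Can Section 8.1 be read inside the limit?** It speaks of dosing beyond cycle 1, never of dosing beyond cycle 8. It contains no cap, however, and the Section 4.5.1 list it leads to contains none. The conflict is by omission, and it is weaker than the PK/ADA conflict, which is explicit in one text section and two tables.

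**5. How many patients might reach the limit?** The documents give no PFS assumption for MGC018. As an illustration only, take the median PFS values of 2.6 and 4.5 months that Section 1.2 cites for lurbinectedin, and assume exponential times.
- 0.5^(7.36/2.6) = 0.14, and 17×0.14 ≈ 2.4 patients.
- 0.5^(7.36/4.5) = 0.32, and 17×0.32 ≈ 5.5 patients.

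That is about 2 to 5 of 17 progression-free at the end of cycle 8. Stopping for toxicity would lower the number on treatment. The continuation past progression that Section 4.5.1 permits in selected cases would raise it.

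**6. Calendar dosing row.** Sections 3.1.1, 3.3.1 and 4.2.2.1 and the dose-level table in Section 4.2.3.1 all give one infusion per 28 days. Appendix 1 Table 4 ties infusion samples to Day 1 and gives Day 15 only a plain blood draw. The Day 15 heading therefore most likely merges visits, and the missing day restriction is an ambiguity.

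**The case against.** The best defence is that the operative sections agree on 8 cycles. Section 8.1 is general wording in the ethics chapter, addressed to patients who comply with the protocol. Section 4.5.1 lists events that force an early stop, so planned completion need not appear there. On this view the PK/ADA rows are a drafting leftover. Much of this stands: Section 8.1 conflicts only by omission. It does not remove the explicit clash with cycles 9 and 12, and it gives a site no rule for choosing.

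The defence is also right about several stronger readings that a reader might draw:

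- *The calendar prescribes a second infusion on Day 15, giving 4 instead of 2 in the first two cycles.* No sentence states a Day 15 infusion, and every dosing statement gives one per 28 days.
- *The limit undermines DOR and PFS.* Section 4.5.1 and the imaging footnote of the study calendar continue tumor assessments for patients who stop for reasons other than progression or loss of benefit, so both remain measurable.
- *Late immunogenicity goes largely unobserved.* Seven scheduled ADA samples and the end-of-treatment sample remain, and no objective in Section 2 names PK or ADA.

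On pregnancy testing, Section 4.4.6 is clear by itself. The calendar's footnote letters skip from f to h, so a row may have been dropped. The mismatch is real but secondary.

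**Conclusion.** The inconsistency is present and should be corrected. Three sections end treatment at 8 cycles; one text section and two tables schedule infusion-linked samples at cycles 9 and 12; and Sections 8.1 and 4.5.1 do not mention the limit. Under the limit, 2 of 10 on-treatment PK/ADA visits (4 PK and 2 ADA samples per patient) cannot occur. Treatment of patients still benefiting after cycle 8 could differ by site, with consequences for exposure and cumulative toxicity.

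The sample counts are exact from the tables and assume only that a patient stays on treatment. The estimate of about 2 to 5 affected patients rests on PFS borrowed from another drug and an exponential shape, and shows only that the case is likely to arise. The primary analysis is not at risk. The treatment row and the absent pregnancy-test row are calendar corrections; neither amounts to a second stated regimen or a contradictory testing rule.

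**What to change.** 1. Reconcile Sections 3.1.1, 3.3.1, 4.2.2.1 and 8.1 to one treatment duration, and refer to it from Section 4.5.1. Which duration is the sponsor's clinical decision.
2. Make Section 3.1.4, its Table 2 and Appendix 1 Table 4 match that duration. If the 8-cycle limit is kept, either delete the cycle 9 and 12 rows or reschedule them to visits that exist.
3. In Appendix 1 Table 2, state the dosing day in the treatment row so that it agrees with Section 4.2.2.1.
4. In the same table, add the per-cycle and post-discontinuation pregnancy tests that Section 4.4.6 already requires.

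**Cost.** Items 1, 3 and 4 are amendment wording and calendar edits, with the approvals described in Section 9.3. Deleting the unreachable rows adds no draws. Rescheduling them in full adds samples that could not be taken under the limit: up to 4 PK and 2 ADA per patient, or at most 17×4 = 68 PK and 17×2 = 34 ADA across the trial.

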8.2 INFORMED CONSENT

The informed consent document must be signed by the subject or the subject's legally authorized representative before his or her participation in the study. The case history for each subject shall document that informed consent was obtained prior to participation in the study. A copy of the informed consent document must be provided to the subject or the subject's legally authorized representative. If applicable, it will be provided in a certified translation of the local language.

Signed consent forms must remain in each subject's study file and must be available for verification by study monitors at any time.

